#### **11.1.2.1. Hypotheses**

There is no pre-specified hypothesis. All the endpoints are descriptive in nature.

#### **11.1.2.2. Statistical Methods**

Lithotripsy procedure cohort: The proportion of subjects who achieved stone clearance at 1 month follow-up post lithotripsy procedure will be calculated.

BPH procedure cohort: The change of IPSS total score at 3-month and 6-month post BPH procedure from baseline will be summarized using descriptive statistics. The same analysis will be performed for subjects with and without catheter at baseline if applicable.

### ***11.2. General Statistical Methods***

#### **11.2.1. Analysis Sets**

The Intent-to-Treat (ITT) subject population includes all subjects who provide written informed consent to be enrolled into the study, and have the Lithotripsy or BPH procedure attempted.

The As Treated (AT) subject population includes all the ITT subjects who had the Lithotripsy or BPH procedure completed.

The Per Protocol (PP) subject population includes all the AT subjects who also meet all eligibility criteria and have no major protocol deviations.

The primary analysis of all the endpoints will be performed for the ITT population. Efficacy endpoints will be evaluated for the PP population as a sensitivity analysis and safety endpoints will be evaluated for the AS population as a sensitivity analysis.

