## 2. Protocol Synopsis

Flexiva Pulse Laser Fiber Post-Market Patient Registry Flexiva Pulse Registry	
Study Objective(s)	To obtain post-market safety and efficacy data for Flexiva™ Pulse High Power Single-Use Laser Fibers during lithotripsy and soft tissue procedure of holmium laser enucleation of the prostate (HoLEP).
Indication(s) for Use	Flexiva Pulse ID and Flexiva Pulse ID TracTip laser fibers are intended to be used as a device that transmits Ho:YAG laser energy from cleared laser consoles to urological anatomy. Flexiva Pulse ID and Flexiva Pulse ID TracTip laser fibers are indicated for urologic applications for which the laser systems are cleared, limited to endoscopic procedures involving vaporization, ablation, hemostasis, coagulation, excision, resection, incision of soft tissue, and lithotripsy of urinary calculi. The fiber is designed for use with a standard SMA-905 connector and has been cleared for surgical use
(Commercial) Device/System applied as Standard of Care and sizes, if applicable	Flexiva Pulse and Flexiva Pulse ID Laser Fibers 

• Flexiva Pulse High Power Single-Use Fiber

• Flexiva Pulse TracTip High Power Single-Use Fiber

• Flexiva Pulse ID High Power Single-Use Fiber and

• Flexiva Pulse ID TracTip High Power Single-Use Laser Fiber

Study Design	Multi-center, open label, prospective study to document on-going post-market safety and performance of Flexiva Pulse High Power Single-Use Laser Fibers.  All subjects meeting the enrollment criteria, signing the consent and undergoing the lithotripsy/HoLEP procedure with the study device(s) will be followed: up to 2 months (60 days) post-discharge from final holmium laser lithotripsy procedure for subjects in the lithotripsy cohort or up to 6 months (180 days + 60 days) post discharge from HoLEP procedure for subjects in the Benign Prostatic Hyperplasia (BPH) cohort.

Flexiva Pulse Laser Fiber Post-Market Patient Registry Flexiva Pulse Registry	
Planned Number of Subjects	Approximately 200 subjects will be enrolled and treated for lithotripsy of urinary calculi and BPH indications. 

• Lithotripsy Cohort – desired number of subjects: 100

• BPH Cohort – desired number of subjects: 100

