**Table 8.2-1: Inclusion Criteria**

Inclusion Criteria	
For Lithotripsy cohort:
 

1. Subject is undergoing treatment for urinary calculi

2. Subject is willing and able to return for all follow-up visits

 
For BPH cohort:
 

1. Subject is <math>\geq 40</math> years of age

2. Subject with a diagnosis of benign prostatic hyperplasia with lower urinary tract symptoms

3. IPSS (International Prostate Symptom) Score <math>\geq 12</math>

4. Qmax (Peak Flow Rate) <math>\leq 15</math> mL/s

5. Subject is willing and able to return for all follow-up visits

---------------------------	---

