## 9. Subject Accountability

### 9.1. *Point of Enrollment*

A subject will be considered enrolled in the study after the subject signs and dates the informed consent form (ICF) and the lithotripsy/HoLEP procedure is attempted. No study specific (non-standard of care) procedure(s) or assessment(s) can take place until the informed consent is signed.

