##### **11.1.1.2. Sample Size**

The sample size justification is based on a confidence interval (CI) approach. As there is limited published literature on the device safety measurement in a clinical study setting, a conservative assumption of 3% SADE rate within 1 month of the procedure for lithotripsy cohort and 5% for BPH cohort within 3 months of the HoLEP procedure was assumed. Ninety

(90) subjects are needed for each cohort to construct a 95% two-sided CI with a maximum width of 8.4% for lithotripsy cohort and 10.2% for HoLEP cohort. Assuming 10% attrition within 1 month of the procedure for lithotripsy cohort and within 3 months of the HoLEP procedure, it is anticipated that 100 treated subjects will be required for each procedure cohort.

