#### **11.1.1.3. Statistical Methods**

A two-sided 95% confidence interval will be constructed using exact (Clopper-Pearson) method to estimate the SADE rate at 30 days post procedure for lithotripsy cohort and the SADE rate at 3-month post procedure for BPH cohort.

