**Table 17.2-1: Safety Definitions**

Term	Definition

Adverse Event (AE)
 
Ref: ISO 14155 Ref: MDCG 2020-10/1
	
Any untoward medical occurrence, unintended disease or injury, or any untoward clinical signs (including an abnormal laboratory finding) in subjects, users or other persons, in the context of a clinical investigation, whether or not related to the study medical device and whether anticipated or unanticipated.
 
NOTE 1: This includes events related to the study medical device or comparator.
 
NOTE 2: This definition includes events related to the procedures involved.
 
NOTE 3: For users or other persons, this definition is restricted to events related to the study medical device.

Adverse Device Effect (ADE)
 
Ref: ISO 14155 Ref: MDCG 2020-10/1
	
Adverse event related to the use of the study medical device
 
NOTE 1: This includes any adverse event resulting from insufficiencies or inadequacies in the instructions for use, the deployment, the implantation, the installation, the operation, or any malfunction of the study medical device.
 
NOTE 2: This definition includes any event resulting from use error or from intentional misuse of the study medical device.
 
NOTE 3: This includes ‘comparator’ if the comparator is a medical device.

Serious Adverse Event (SAE)
 
Ref: ISO 14155 Ref: MDCG 2020-10/1
	
Adverse event that led to any of the following:
 
a) death,
 
b) serious deterioration in the health of the subject, users or other persons as defined by either:
 
 
1) a life-threatening illness or injury, or
 
2) a permanent impairment of a body structure or a body function, including chronic diseases, or
 
3) in-patient hospitalization or prolongation of existing hospitalization, or
 
4) medical or surgical intervention to prevent life-threatening illness or injury or permanent impairment to a body structure or a body function
 
 
c) fetal distress, fetal death, or a congenital abnormality or birth defect including physical or mental impairment.
 
NOTE 1: Planned hospitalization for a pre-existing condition, or a procedure required by the clinical investigational plan, without a serious deterioration in health, is not considered a serious adverse event.

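### The primary SADE denominator is not tied to use of the study fiber, so a subject in whom no Flexiva Pulse fiber was used would dilute the device's safety rate

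*Combined protocol and SAP*

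**What the plan says.** The rules that decide who is counted do not mention the fiber:

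- **Eligibility (Table 8.2-1 and synopsis).** The first lithotripsy criterion is "Subject is undergoing treatment for urinary calculi". The BPH list covers age, diagnosis, IPSS, Qmax and willingness to return.
- **Enrollment (9.1; similarly 7.2 and 9.4).** Consent and an attempt at the procedure suffice: "A subject will be considered enrolled in the study after the subject signs and dates the informed consent form (ICF) and the lithotripsy/HoLEP procedure is" (the final word of that sentence asks only for an attempt).
- **Analysis sets (11.2.1).** The ITT set "includes all subjects who provide written informed consent to be enrolled into the study, and have the Lithotripsy or BPH procedure attempted", and it is primary for all endpoints. The As Treated set adds only that the procedure was completed.
- **Start of the procedure (10.6).** The procedure runs from the start of sedation or anesthesia, which comes before any fiber is introduced.

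Other text does tie the registry to the device. In the synopsis, consenting subjects "undergoing the lithotripsy/HoLEP procedure with the study device(s) will be followed". Section 10.2.1 recruits patients who receive the device as standard of care, and section 11.2.2 opens the registry to those planning a procedure with the fibers. Sections 10.6 and 10.10 take a subject out of the study when an additional lithotripsy procedure does not use the study fiber.

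The endpoint depends on the device. Table 17.2-1 defines an adverse device effect as "Adverse event related to the use of the study medical device", and a SADE is the serious form of it.

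**The concern.** The condition that links a subject to the device appears in descriptive text but not in the definitions that fix the denominator. Two kinds of subject fall in the gap: one whose procedure is stopped after anesthesia but before a fiber is used, and one whose index procedure is carried out with a different fiber. Both count as enrolled and ITT as the text stands. The exit rule does not reach them, because it concerns only an additional procedure.

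Such a subject adds one to the denominator and should add nothing to the numerator. The primary safety result is meant to describe the fiber, and any dilution can only make the fiber look safer. Section 11.2.2 calls the exact interval conservative, and this effect works against that aim.

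**Working it through.** **Inputs.** From 11.1.1.3: "A two-sided 95% confidence interval will be constructed using exact (Clopper-Pearson) method to estimate the SADE rate at 30 days post procedure" in the lithotripsy cohort, and at 3 months in the BPH cohort. From 11.1.1.2: "a conservative assumption of 3% SADE rate within 1 month of the procedure for lithotripsy cohort"; for BPH, a rate of 5% at 3 months; 90 evaluable subjects per cohort; 10% attrition; 100 treated per cohort. The share *u* of ITT subjects with no study fiber used is not in the documents. I assume a range that starts at 0 and show 5% and 10%.

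**Step 1: the plan's own figures.** For *x* events in *n* subjects, the Clopper-Pearson limits are the 2.5% quantile of Beta(*x*, *n* − *x* + 1) and the 97.5% quantile of Beta(*x* + 1, *n* − *x*).

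- Lithotripsy: *x* = 90 × 0.03 = 2.7 gives 0.55% to 8.95%, width 8.40 points.
- BPH: *x* = 90 × 0.05 = 4.5 gives 1.52% to 11.75%, width 10.23 points.
- Attrition: 90 / 0.90 = 100.

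These match the stated 8.4%, 10.2% and 100. The sample size calculation is not in question.

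**Step 2: dilution of the expected rate.** If unexposed subjects cannot have a SADE, observed rate = true rate × (1 − *u*).

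| True rate | *u* = 0 | *u* = 5% | *u* = 10% |
|---|---|---|---|
| 3% (lithotripsy) | 3.00% | 2.85% | 2.70% |
| 5% (BPH) | 5.00% | 4.75% | 4.50% |

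The rate falls by 0.15 to 0.30 points in lithotripsy and by 0.25 to 0.50 points in BPH.

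**Step 3: the same events over exposed subjects only.**

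| Events | All 100 ITT | 95 exposed | 90 exposed |
|---|---|---|---|
| 3 | 3.00% (0.62 to 8.52) | 3.16% (0.66 to 8.95) | 3.33% (0.69 to 9.43) |
| 5 | 5.00% (1.64 to 11.28) | 5.26% (1.73 to 11.86) | 5.56% (1.83 to 12.49) |
| 0 | 0% (upper 3.62) | 0% (upper 3.81) | 0% (upper 4.02) |

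With no events the estimate does not move; only the upper limit does.

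**Step 4: starting from 90 evaluable subjects.** Removing 5% or 10% leaves about 86 or 81. The upper limit for 3 events goes from 9.43% to 9.86% or 10.44%; for 5 events, from 12.49% to 13.05% or 13.82%. The picture is the same.

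**Step 5: would the planned sensitivity analysis show it?** Section 11.2.1 repeats the safety analysis in a set printed as AS, read here as As Treated. That set keeps a procedure completed with another fiber. It also drops an exposed subject whose procedure was stopped, including one stopped because of a device-related event. It therefore does not separate exposed from unexposed. The glossary in 23.2 defines ITT and As Treated differently from 11.2.1, but neither version mentions the fiber.

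**The case against.** The strongest reply is that the protocol already limits the registry to the device. Section 11.2.2 directly follows the analysis sets and names subjects planning a procedure with the fibers. Section 10.2.1 and the synopsis agree, and section 10.6 has the procedure performed under the fiber's instructions for use. This stands in large part. A reader might infer from the inclusion lists and the ITT definition that the registry is open to anyone having stone or prostate surgery, or that unexposed subjects are known to enter. The documents support neither reading. What they leave open is narrower: the fiber was planned but not used, and no section says how to count that subject.

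A reader might also infer that a stone cleared without the fiber would be credited to the device as stone-free. The definition in 11.1.2 does not support this. It runs from the final Flexiva Pulse lithotripsy procedure, and a subject with no such procedure has no starting point and does not meet the definition as written.

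Two further objections hold in part. The As Treated set does remove procedures abandoned before fiber use, but with the faults shown in step 5. And with no hypothesis or performance threshold (11.1.1.1), a shift of a few tenths of a point changes no formal decision.

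A last objection concerns the remedy. Table 17.2-1 counts events from deployment, installation or malfunction as device effects, so a denominator limited to subjects in whom a fiber was introduced could lose a true case that arose earlier. That is right, and the fix below allows for it.

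**Conclusion.** The point holds as a gap in the denominator. The primary SADE rate is computed over subjects with an attempted procedure, whether or not the study fiber was used, and no analysis set is defined by exposure. The direction is certain, provided that a SADE cannot properly be assigned where no study fiber was involved: the rate, its upper limit, or both are lowered.

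The size is modest and rests on an assumed share. At 5-10% unexposed, the expected rate falls by 0.15 to 0.50 points and the upper limit for 3 or 5 events in 100 is understated by about 0.4 to 1.2 points, against planned widths of 8.4 and 10.2. If every attempted procedure used a study fiber, the effect is nil. The change is worth making because it corrects the primary safety rule at almost no cost, not because the result is likely to move far.

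**What to change.** 1. In 11.1.1.3 and 11.2.1, define the primary SADE denominator as ITT subjects in whom at least one Flexiva Pulse or Flexiva Pulse ID fiber was opened or used at any study procedure, whether or not the procedure was completed. Including opened fibers keeps device effects that arise before introduction.
2. Keep the SADE rate in the full ITT set as a supportive analysis.
3. In the disposition table, report by cohort the number of attempted procedures with no study fiber, separating those stopped before fiber use from those done with another fiber.
4. Add planned use of a study fiber to both inclusion lists in Table 8.2-1 and the synopsis, so that they agree with 11.2.2.

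Section 10.6 already collects fiber type and the number used. At most, a line in the form instructions is needed so that a fiber opened but not used is recorded. The cost is a possibly smaller denominator and a slightly wider interval: for 3 events, the width goes from 7.89 points at 100 subjects to 8.74 at 90; for 5 events, from 9.64 to 10.66.

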**Figure 7.1-1: Flexiva Pulse Laser Fiber Post-Market Registry Study Design**

## 7.2. Treatment Assignment

This is a post-market registry study. Any subject who is indicated for lithotripsy or BPH undergoing HoLEP and is willing to provide a written informed consent will be approached and considered for enrollment in the study. The subject is considered enrolled in the study once the subject has signed the informed consent form and the lithotripsy/HoLEP procedure is attempted. Each subject will be assigned a unique subject identifier in the Electronic Data Capture (EDC) system.

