**Table 23.2-1: Definitions**

Term	Definition
Adverse Device Effect (ADE)	See Table 17.2-1: Safety Definitions
Adverse Event (ADE)	See Table 17.2-1: Safety Definitions
As Treated	All subjects for whom treatment is attempted.
Clinical Events Committee	An independent or group of physicians with trial relevant therapeutic expertise whose purpose is to review and adjudicate important endpoints and/or specific adverse events.
Data Subject	In GDPR: Any living individual to whom the personal data relates. Examples of data subjects in this study are physicians and subjects.

Term	Definition
Deviation (Clinical Protocol)	A departure from the requirements established in the clinical trial protocol (e.g., inclusion/exclusion criteria; visit windows, required procedures, and any specified consenting process requirements).
Device Deficiency	See Table 17.2-1: Safety Definitions
General Data Protection Regulation (GDPR)	The General Data Protection Regulation (GDPR) is a European law that will govern how companies (whether EU-based or not) use personal data.
Hospitalization	See Table 17.2-1: Safety Definitions
Intent-To-Treat	A subject who signs the informed consent, meets eligibility criteria, and for whom the Lithotripsy/HoLEP procedure is initiated but not completed (first incision). The original ICF and screening documentation for intent to treat patients should be maintained in the site's files. These patients are followed in accordance with the study follow up schedule for safety and count toward enrollment.
Monitoring	EN ISO 14155:2020-3.29 - Act of overseeing the progress of a clinical investigation to ensure that it is conducted, recorded, and reported in accordance with the CIP, written procedures, this document, and the applicable regulatory requirements.  ICH E6 1.38 - The act of overseeing the progress of a clinical study and of ensuring that it is conducted, recorded, and reported in accordance with the protocol, Standard Operating Procedures (SOPs), GCP, and the applicable regulatory requirement(s).  FDA Guidance - Generally refers to the methods used by sponsors of investigational studies, or CROs delegated responsibilities for the conduct of such studies, to oversee the conduct of and reporting of data from clinical investigations, including appropriate investigator supervision of study site staff and third-party contractors.

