Multi-center study	A clinical trial conducted according to a single protocol but at more than one site, and therefore carried out by more than one investigator.
Per Protocol	All subjects in the As Treated Population who have no major protocol deviations.
Personal Data	GDPR defines "Personal data" to be any information relating to an identified or identifiable natural person ('data subject'); an identifiable natural person is one who can be identified, directly or indirectly, in particular by reference to an identifier such as a name, an identification number, location data, an online identifier or to one or more factors specific to the physical, physiological, genetic, mental, economic, cultural or social identity of that natural person.
Point of Enrollment	Time at which, following recruitment, a subject signs and dates the informed consent form
Processing	Any use of personal data by BSC (or a third party on behalf of BSC), including data collection, data sharing, anonymization, and data storage (note the mere storage of data is considered as processing).

Term	Definition
RAVE	Proprietary electronic data capture system for capturing, managing and reporting clinical study data.
Recruitment	Active efforts to identify subjects who may be suitable for enrollment in the clinical investigation.
Sensitive Personal Data	GDPR defines “Sensitive personal” data as a subset of Personal Data, which, due to their nature have been classified as deserving additional privacy and security protections because their processing may create a risk for an individual’s fundamental right and freedom.
Serious Adverse Device Effect (SADE)	See Table 17.2-1: Safety Definitions
Serious Adverse Event (SAE)	See Table 17.2-1: Safety Definitions
Site Noncompliance	A departure from the regulations established by the relevant regulatory authorities. Includes all clinical site noncompliance that does not represent a direct deviation from the clinical trial protocol, e.g. IRB/IEC and sponsor reporting, device storage and accountability, staff qualifications and training, facilities, and equipment required to conduct the clinical trial, collection and documentation of data in source documents and CRFs, investigator oversight, etc.
Source Document	Original or certified copy of printed, optical or electronic document containing source data ( Ref. ISO 14155-2020 )

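### Section 11.2.1 and Table 23.2-1 define ITT, As Treated and enrollment incompatibly, and the Per Protocol analysis of procedure completion cannot register an aborted procedure

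*Combined protocol and SAP*

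**What the plan says.** Section 11.2.1 defines three nested sets. ITT is every consented subject with an attempted procedure. AT is the finished part of ITT: "The As Treated (AT) subject population includes all the ITT subjects who had the Lithotripsy or BPH procedure completed". PP is AT restricted to eligible subjects without major deviations. ITT is primary for all endpoints, PP is the sensitivity set for efficacy, and a set called AS is the sensitivity set for safety.

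Table 23.2-1 defines the same terms again. AT is "All subjects for whom treatment is attempted". ITT is a subject who consents, is eligible, and "for whom the Lithotripsy/HoLEP procedure is initiated but not completed (first incision"). The entry adds: "These patients are followed in accordance with the study follow up schedule for safety and count toward enrollment". PP is "All subjects in the As Treated Population who have no major protocol deviations". Point of Enrollment is "Time at which, following recruitment, a subject signs and dates the informed consent form", whereas 7.2 says "The subject is considered enrolled in the study once the subject has signed the informed consent form and the lithotripsy/HoLEP procedure is attempted", and 9.1 and 9.4 agree with 7.2.

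Secondary efficacy endpoint 1 (11.3.1.2) is whether the index procedure was successfully completed, reported as a proportion of subjects. Endpoint 2 (11.3.1.3) is the proportion of fibers compatible with the endoscope. Endpoint 5 (11.3.1.6) is the proportion of HoLEP subjects in whom hemostasis was achieved.

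**The concern.** The set used for the primary analysis of every endpoint has two definitions in one document, and nothing says which prevails. They differ in two ways: whether finished procedures belong in ITT, and whether a treated but ineligible subject does. AT is also defined in two opposite ways, so reading AS as AT does not by itself settle who enters the safety sensitivity analysis.

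A second problem remains even if 11.2.1 governs. Endpoint 1 asks whether the procedure was finished successfully, and PP admits only subjects whose procedure was finished. The set is selected on a large part of the outcome that it is meant to check. A reader who compares PP with ITT for reassurance would be comparing it with a figure from which the aborted procedures have been removed.

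**Working it through.** **Definitions side by side**

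| Term | Section 11.2.1, or 7.2, 9.1 and 9.4 | Table 23.2-1 |
|---|---|---|
| ITT | Consent, procedure attempted | Consent, eligible, procedure started but not finished |
| AT | ITT and procedure finished | Treatment attempted |
| PP | AT, eligible, no major deviation | AT, no major deviation |
| Enrollment | Consent and procedure attempted | Consent only |
| AS | Named, not defined | Absent, also from the abbreviations |

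The PP difference is mainly inherited from AT. The Table drops the eligibility clause, but its own definition of a deviation covers eligibility: "A departure from the requirements established in the clinical trial protocol (e.g., inclusion/exclusion criteria; visit windows, required procedures".

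If the Table's ITT is put into the AT rule of 11.2.1 (ITT and finished), AT is empty, and so is PP.

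**The plan's own figures**

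Inputs from 11.1.1.2: n = 90, SADE rates of 3% and 5%, 10% attrition. The Clopper-Pearson limits are lower = Beta(0.025; x, n−x+1) and upper = Beta(0.975; x+1, n−x). With x = np = 2.7 and 4.5, the widths are 8.40% and 10.23%, which match the stated 8.4% and 10.2%. Treated n = 90/0.9 = 100, as stated. The definitions do not affect this arithmetic.

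**Completion under 11.2.1**

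The documents give no abort rate. I assume a = 2, 5 or 10 aborted among n = 100 attempted, u finished cases scored unsuccessful, and no other PP exclusions. Then

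- ITT completion = (n − a − u)/n
- PP completion = (n − a − u)/(n − a) = 1 − u/(n − a)

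With u = 0, PP is 1 whatever the value of a.

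| Aborted | ITT, u = 0 (95% CI) | PP, u = 0 | ITT, u = 2 | PP, u = 2 | ITT, u = 10 | PP, u = 10 |
|---|---|---|---|---|---|---|
| 2 | 98.0% (93.0–99.8) | 98/98 = 100% | 96.0% | 96/98 = 98.0% | 88.0% | 88/98 = 89.8% |
| 5 | 95.0% (88.7–98.4) | 95/95 = 100% | 93.0% | 93/95 = 97.9% | 85.0% | 85/95 = 89.5% |
| 10 | 90.0% (82.4–95.1) | 90/90 = 100% | 88.0% | 88/90 = 97.8% | 80.0% | 80/90 = 88.9% |

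From 2 to 10 aborts, ITT falls by 8 points in every scenario. PP falls by 0, 0.2 and 0.9 points. PP responds to u and hardly at all to a.

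**Other results touched by the same exclusion**

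A fiber fracture, a failed passage or a bleed that ends the procedure removes that subject from PP, and with it a failure on endpoint 2 or 5. A SADE in an aborted procedure stays in ITT but leaves AT as 11.2.1 defines it. The documents give nothing from which to size these losses.

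**The case against.** The strongest reply is that little turns on the contradiction. Section 11.2.1 is the operative text and names the set for each analysis, 7.2, 9.1 and 9.4 support it, and the conflict sits in a closing glossary. The Table's ITT entry may only be a reminder that unfinished cases are still followed and counted. AS looks like a slip for AT, which is defined a few lines above it. No hypothesis is tested, and the full-denominator ITT result will be reported as primary. All of this is fair and limits the weight of the point. It does not remove it: as worded, the Table's ITT entry excludes every finished procedure and adds an eligibility condition, and no text gives precedence.

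A reader might infer that PP completion is near 100% by construction. The documents do not support that without a condition. They do not equate *completed* (the AT rule) with *successfully completed* (endpoint 1), and 11.2.1 does not require completion with the study fiber. A case finished despite a fiber failure could be in PP and score as unsuccessful. With 10 such cases PP is about 89% to 90%, so it can register some failures. What stands is narrower: it cannot register aborted procedures.

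**Conclusion.** The concern holds in this form. The contradictions over ITT (including eligibility), AT and Point of Enrollment, and the undefined AS, can be read directly from the text. Under 11.2.1, the PP analysis of endpoint 1 excludes every aborted procedure. If *completed* and *successfully completed* are scored alike, PP is 100% at any abort rate, against ITT values of 98.0%, 95.0% and 90.0% for 2, 5 and 10 aborts per 100. If they are scored differently, PP measures only failures among finished cases. The abort counts and the numbers of unsuccessful finished cases are assumptions, as is the absence of other PP exclusions.

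It would be tempting to conclude that the primary results are compromised, because the Table read literally leaves only the 2, 5 or 10 aborted subjects in ITT (if all are eligible), with 0% completion. The rest of the protocol points to 11.2.1, and under it the primary ITT estimates are unaffected. No size is claimed for endpoints 2 and 5 or for the AT safety analysis.

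**What to change.** 1. State that 11.2.1 and 9.1 govern. Correct the ITT entry (including its eligibility clause) and the AT, PP and Point of Enrollment entries in Table 23.2-1 to match.
2. Change AS to AT in 11.2.1.
3. Report secondary efficacy endpoint 1 in ITT only. Label the PP results for endpoints 2 and 5, and the AT safety results, as conditional on a completed procedure.

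These are wording changes that need no new data, subjects or visits. Section 11.3.7 already provides for documenting changes before the analyses are run. The only loss is one sensitivity result that cannot count aborted procedures.

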## **11. Statistical Considerations**

### **11.1. *Endpoints***

#### **11.1.1. Primary Safety Endpoint**

The primary safety endpoint is the occurrence of any Serious Adverse Device Effects (SADE) (including burn, perforation, and hemorrhage) during Lithotripsy and BPH procedures.

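### The safety sensitivity set keeps only completed procedures, so it can drop subjects whose SADE stopped the case and understate the SADE rate

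*Combined protocol and SAP*

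**What the plan says.** Section 11.2.1 defines three sets. ITT is consented subjects who "have the Lithotripsy or BPH procedure attempted". For the next set, "The As Treated (AT) subject population includes all the ITT subjects who had the Lithotripsy or BPH procedure completed". Per Protocol is a subset of AT.

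On their use, the same section says "The primary analysis of all the endpoints will be performed for the ITT population", and then that "safety endpoints will be evaluated for the AS population as a sensitivity analysis". The label AS is defined nowhere in the documents. AT is the only defined set that fits, and it is read that way here.

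Section 11.1.1 gives the primary safety endpoint as "the occurrence of any Serious Adverse Device Effects (SADE) (including burn, perforation, and hemorrhage) during Lithotripsy and BPH procedures".

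Table 23.2-1 defines As Treated differently, as "All subjects for whom treatment is attempted", with no completion condition. The same table describes an Intent-To-Treat subject as one whose procedure was started but not completed, which also disagrees with Section 11.2.1.

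**The concern.** Membership of the AT set in Section 11.2.1 is decided after exposure to the device. The endpoint names burn, perforation and hemorrhage during the procedure, and an event of that kind may be why a case is not finished. A subject harmed in this way counts in ITT and disappears from the safety sensitivity analysis, so the set is partly selected on the outcome it is meant to measure. The plan itself treats completion as an outcome: Section 11.3.1.2 makes successful completion a secondary efficacy endpoint in both cohorts.

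What is at stake is how the sensitivity result is read. At the planning rates only 3 to 5 SADEs are expected per 100 subjects, so losing one or two visibly changes the rate and its upper limit. A lower AT rate could be taken as reassurance when it only reflects who was removed.

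**Working it through.** **Inputs from the documents.** Planning SADE rates are 3% for lithotripsy (1 month) and 5% for BPH (3 months), with 90 evaluable subjects per cohort, 10% attrition and 100 treated subjects per cohort (Section 11.1.1.2). Intervals are two-sided 95% Clopper-Pearson (Section 11.1.1.3).

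**Assumed, because the documents do not give them.** These are the number of procedures attempted but not completed, and how many of those subjects have a SADE. That an intraprocedural SADE can stop a case is a clinical inference; the documents do not state it.

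**Step 1: reproduce the plan's figures.** For x events in n subjects, the lower limit is the 0.025 quantile of Beta(x, n − x + 1) and the upper limit is the 0.975 quantile of Beta(x + 1, n − x). Using x = n × rate:
- 3% of 90 (x = 2.7): 0.55% to 8.95%, width 8.40%. The plan states 8.4%.
- 5% of 90 (x = 4.5): 1.52% to 11.75%, width 10.23%. The plan states 10.2%.
- 90 / (1 − 0.10) = 100 per cohort, as stated.

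The sample size reproduces and is not in question.

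**Step 2: the effect of the completion condition.** Let ITT have N subjects, X of them with a SADE. Let a subjects be non-completed, k of them with a SADE. Then

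ITT rate = X / N, and AT rate = (X − k) / (N − a).

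The AT rate is below the ITT rate exactly when k / a > X / N, that is, when SADEs are more common among non-completed cases than overall.

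**Step 3: numbers, with N = 100.**

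| Cohort and assumption | Rate | Upper 95% limit |
|---|---|---|
| Lithotripsy, ITT, X = 3 | 3/100 = 3.00% | 8.52% |
| a = 1, k = 1 | 2/99 = 2.02% | 7.11% |
| a = 2, k = 2 | 1/98 = 1.02% | 5.55% |
| a = 3, k = 3 (extreme) | 0/97 = 0% | 3.73% |
| a = 11, k = 1 | 2/89 = 2.25% | 7.88% |
| a = 10, k = 0 | 3/90 = 3.33% | 9.43% |
| BPH, ITT, X = 5 | 5/100 = 5.00% | 11.28% |
| a = 1, k = 1 | 4/99 = 4.04% | 10.02% |
| a = 2, k = 2 | 3/98 = 3.06% | 8.69% |
| a = 11, k = 1 | 4/89 = 4.49% | 11.11% |
| a = 10, k = 0 | 5/90 = 5.56% | 12.49% |

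**Step 4: where the direction turns, with one SADE-stopped case.**
- Lithotripsy: 2 / (100 − a) < 3/100 requires 100 − a > 66.7, so AT stays below ITT up to 33 non-completions per 100.
- BPH: 4 / (100 − a) < 5/100 requires 100 − a > 80, so AT stays below ITT for fewer than 20 non-completions and equals it at 20.

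**Step 5: the competing definition.** Under the Table 23.2-1 wording of As Treated, a = 0 by construction. The sensitivity result then equals ITT: 3/100 (0.62% to 8.52%) and 5/100 (1.64% to 11.28%).

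**The case against.** The strongest reply has four parts.

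- **The primary result is protected.** ITT in Section 11.2.1 needs only an attempted procedure, so SADE-stopped subjects stay in the main rate and interval. There is no hypothesis test. Only a descriptive secondary figure, printed beside the ITT figure, is touched. This stands and limits the weight of the point. A reader might infer that the headline SADE rate is biased; under Section 11.2.1 it is not.
- **The direction is not fixed.** A reader might infer that the AT rate can only look better. Step 2 shows otherwise: SADE-free non-completions raise it, for example from 3.00% to 3.33%. This stands. Understatement needs at least one SADE-stopped subject and, at these rates, fewer non-completions than the Step 4 limits.
- **The scenarios are assumed.** The planning rates cover events up to 1 and 3 months, and an event after a completed procedure cannot have stopped it. Losing all three lithotripsy SADEs is therefore an extreme. This stands.
- **The definition is unsettled.** If Table 23.2-1 prevails, nobody is removed. That is true, but Section 11.2.1 is the text that assigns sets to analyses, so the conflict has to be resolved rather than assumed away.

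It would also be too strong to say that agreement between the two sets tells the reader nothing. An equal SADE count shows that no SADE subject was excluded. Completion proportions and event counts by seriousness and device relatedness are already planned (Sections 11.3.1.2.1 and 11.3.1.1.1), but nothing in the plan links the two.

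**Conclusion.** The point holds in a limited form. As Section 11.2.1 is written, and reading AS as AT, the safety sensitivity analysis drops any subject whose SADE prevented completion and so can understate the SADE rate. On the stated assumptions, one such subject moves lithotripsy from 3.0% to 2.0% (upper limit 8.5% to 7.1%), and two move BPH from 5.0% to 3.1% (upper limit 11.3% to 8.7%). The lithotripsy extreme is 0% (upper limit 3.7%). If non-completions carry no SADE, the rate moves the other way by a smaller amount, to 3.3% or 5.6% with ten of them. Either shift comes from selection on completion and says nothing about the robustness of the SADE rate.

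The primary ITT analysis and the sample size are unaffected. The change should be made because the rule builds selection on the outcome into a safety analysis and is cheap to remove, but it does not threaten the study's main result. The size depends on how many procedures are stopped and why, which the documents do not give.

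**What to change.** 1. In Section 11.2.1, remove completion as a condition for the safety sensitivity set. Define the set as all enrolled subjects in whom a Flexiva Pulse fiber was introduced, whether or not the procedure was completed.
2. Replace the label AS with the name of that set, and reconcile the As Treated and Intent-To-Treat definitions in Section 11.2.1 and Table 23.2-1. Per Protocol is built on AT, so state how it follows from the revised wording.
3. Add a listing of every non-completed procedure with its reason and any SADE.

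A completed-only set should not simply be moved to efficacy. Successful completion is itself a secondary efficacy endpoint and would be close to 100% by construction in such a set.

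The cost is a short text edit and one listing, with no new subjects or visits. Section 10.6 already collects fiber use and adverse events at the procedure. The reason for stopping is not named there as a data item, so its availability in the procedure records should be confirmed. Section 11.3.7 provides for an amended SAP before the analyses are run. The downside is that the new set may nearly coincide with ITT and add little as a separate analysis; the listing would then carry most of the information.
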